Slight to moderate periorbital swelling was observed primarily during the recovery phase in all IMC-CS4-treated groups. This clinical sign has been reported to occur in humans with another antibody to CSF-1 (Sadis et al. 2009), and may thus represent a delayed response to IMC-CS4 in the treated monkeys. Watery feces was observed only in the 60-mg/kg/dose animals, but is considered possibly related to the administration of IMC-CS4. These clinical signs were not considered adverse based on their limited impact to the overall health of the animal.

Based on the absence of any definitive IMC-CS4-related adverse findings, the NOAEL for IMC-CS4 administered via 15-minute I.V. infusion qw on 4 occasions was considered to be 180 mg/kg/dose (Day 22 mean C_{max} of 7985 $\mu\text{g}/\text{mL}$, $C_{168\text{hr}}$ of 2945 $\mu\text{g}/\text{mL}$, and mean $AUC_{0-168\text{hr}}$ of 711340 $\mu\text{g}\cdot\text{hr}/\text{mL}$).

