7.3 End-of-Therapy Evaluations

End-of-therapy evaluations will be assessed on subjects who are no longer receiving study therapy. The end-of-therapy evaluations will include:

- ECG (triplicate ECG for Part A only, as described in Sections 6.9.1 and 7.2.3.1);
- ECOG PS assessment;
- Physical examination;
- Vital signs (including temperature, pulse rate, respiration rate, and blood pressure);
- Weight measurement;
- Toxicity/AE evaluations;
- Concomitant medication assessment;
- Hematology profile;
- Serum chemistry profile;
- C-reactive protein assessment;

- Troponin (I or T) analysis and isoenzyme assessment of LDH, CK, and AP only if serum enzymes are $\geq 2.5 \times$ ULN at Week 5 of Cycle 1; and
- Urinalysis.

In cases of tumor progression, if the subject's condition allows it, a (core needle or excisional) biopsy of the tumor will be performed. For subjects who discontinue study therapy for any reason other than PD, every effort will be made to obtain radiographic tumor assessments at 6 and 12 weeks following the first dose of study therapy and/or until radiographic documentation of PD.

7.4 30-Day Follow-up Evaluations

All subjects will be followed for a minimum of 30 days after the last dose of study therapy; AEs occurring during this period will be documented and reported according to the guidelines in Section 8. A follow-up evaluation will be conducted approximately 30 days (+0-7 days) after the last dose of study therapy, and will include:

- Serum β -hCG pregnancy test in WOCBP;
- ECOG PS assessment;
- Physical examination;
- Vital signs (including temperature, pulse rate, respiration rate, and blood pressure);
- Weight measurement;
- Toxicity/AE evaluations;
- Concomitant medication assessment;
- Hematology profile;
- Serum chemistry profile, including myoglobin;
- C-reactive protein assessment;
- Troponin (I or T) analysis and isoenzyme assessment of LDH, CK, and AP only if serum enzymes are $\geq 2.5 \times$ ULN at Week 5 of Cycle 1;
- Urinalysis;
- Blood samples for PK, immunogenicity, and pharmacodynamic evaluations; and
- Blood sample for flow cytometry analysis of peripheral leukocytes.

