8.1 Adverse Events

The Sponsor has standards for reporting AEs that are to be followed regardless of applicable regulatory requirements that may be less stringent. A clinical study AE is any untoward medical occurrence in a patient or clinical investigation subject administered a pharmaceutical product and which does not necessarily have a causal relationship with this treatment. Any clinically significant findings from ECGs, laboratory assessments, vital sign measurements, or other procedures that result in a diagnosis should be reported to the Sponsor or its designee.

Lack of drug effect is not an AE in clinical trials, because part of the purpose of a clinical trial is to establish drug effect.

Cases of pregnancy that occur during maternal or paternal exposures to study treatment and up to 12 weeks following last study treatment dose should be reported immediately. Data on fetal outcome and breastfeeding are collected for regulatory reporting and drug safety evaluation.

For all entered subjects, study site personnel will record the occurrence and nature of each subject's preexisting conditions, including clinically significant signs and symptoms of the disease under treatment in the study. While the subject is on study, site personnel will record any change in these preexisting condition(s) and the occurrence and nature of any AEs. In addition, all AEs related to protocol procedures are reported to the Sponsor or designee.

In addition, all AEs occurring after the subject receives the first dose of study treatment until 30 days following the discontinuation of study treatment must be reported to the Sponsor or its designee via eCRF.

Investigators will be instructed to report to the Sponsor or its designee their assessment of the potential relatedness of each AE to protocol procedure or investigational product via eCRF.

The Investigator will decide whether he or she interprets the observed AEs as related to disease, to the study medication, study procedure, or other concomitant treatment or pathologies. To assess the relationship of the AE to the study drug or procedure, the following terminologies are defined:

- **Probably related:** A direct cause and effect relationship between the study treatment and the AE is likely.
- **Possibly related:** A cause and effect relationship between the study treatment and the AE has not been demonstrated at this time and is not probable, but is also not impossible.

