Serious adverse events occurring after a subject has taken the last dose of study treatment will be collected for 30 days after the discontinuation of study treatment, regardless of the Investigator's opinion of causation. Thereafter, SAEs are not required to be reported unless the Investigator feels the events were related to either study treatment or a protocol procedure.

Data on SAEs that occur before the end of trial will be stored in the collection database and the Lilly Safety System. If an Investigator becomes aware of an SAE occurring after the subject's participation in the trial has ended, and the Investigator believes that the SAE is related to a protocol procedure or study drug, the Investigator should report the SAE to the Sponsor, and the SAE will be entered into the Lilly Safety System.

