12.5.2 Safety Analysis

The number of subjects who experience any DLT will be presented based on all DLT-evaluable subjects (DLT population). All other safety analyses will be performed using the safety population (that is, all subjects who received any dose of study therapy).

All subjects will be assessed regularly for potential occurrence of AEs from the time that the subject provides informed consent, until 30 days after the last dose of study therapy. An AE will be regarded as treatment-emergent if its onset date occurs: any time after the administration of the first dose of study medication, up to 30 days after the last dose of study medication (or up to any time if related to study medication), or prior to first dose date and worsens while on study medication.

AEs will be summarized by MedDRA System Organ Class and Preferred Term, classified from verbatim terms. The incidence and percentage of subjects with at least one occurrence of a Preferred Term will be included, according to the most severe NCI-CTCAE, Version 4.0 grade. Causality (relationship to study drug) will be summarized separately.

All treatment-emergent AEs, SAEs, and NCI-CTCAE, Version 4.0 Grade 3 or higher AEs; related AEs, SAEs, and NCI-CTCAE, Version 4.0 Grade 3 or higher AEs; AEs leading to dose modification and study medication discontinuation; and deaths will be summarized according to MedDRA Preferred Terms. Duration of AE will be determined and included in listings along with action taken and outcome.

Laboratory results will be classified according to NCI-CTCAE, Version 4.0. Laboratory results not corresponding to an NCI-CTCAE, Version 4.0 term will not be graded. Laboratory toxicity shifts from baseline to worst grade will be provided. The last measurement before study medication will serve as the baseline measurement. Results for variables that are not part of the NCI-CTCAE, Version 4.0 will be presented in the listings as below, within, or above the normal limits of the local laboratory.

The results from physical examination, vital sign measurement, and other assessments will be tabulated, if appropriate.

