5.2.1.2 Treatment-Emergent Adverse Events

An AE will be regarded as **treatment-emergent** if its onset date occurs any time after the administration of the first dose of study medication, up to 30 days after the last dose of study medication (or up to any time if related to study medication), or if it occurs prior to first dose date and worsens while on study medication.

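### The treatment-emergent rule counts new adverse events to 30 days after the last dose but counts worsening of earlier ones only on study medication, although both are collected to Day 30

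*Protocol*

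**What the plan says.** **Collection.** Protocol Section 8.1 requires that all AEs from the first dose "until 30 days following the discontinuation of study treatment must be reported to the Sponsor or its designee via eCRF". It also has site staff record any change in preexisting conditions for as long as the subject is on study. Section 7.4 agrees: "All subjects will be followed for a minimum of 30 days after the last dose of study therapy", with AEs in that period documented and reported. Section 12.5.2 describes AE assessment from consent "until 30 days after the last dose of study therapy". Beyond 30 days, Section 8.2 narrows the duty: "Thereafter, SAEs are not required to be reported unless the Investigator feels the events were related to either study treatment or a protocol procedure".

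**Counting.** Protocol 12.5.2 treats an AE as treatment-emergent if it starts after the first dose and no later than 30 days after the last dose. The sentence then adds, in parentheses and after, "or up to any time if related to study medication), or prior to first dose date and worsens while on study medication". SAP 5.2.1.2 has the same rule; its last limb reads "or if it occurs prior to first dose date and worsens while on study medication".

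**The concern.** A single sentence applies two post-dose windows. New events have 30 days after the last dose, and longer if related. Events that began before the first dose have only the time on study medication, a term that neither document defines. The data for both kinds of event are collected over the same period.

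The case is an ordinary one. Inclusion criterion 3 admits subjects with residual toxicity up to Grade 1, and Section 6.2 uses Grade 1 fatigue as its example of a preexisting toxicity to be graded at baseline. If such fatigue reaches Grade 3 ten days after the last dose, the literal rule leaves it out. Fatigue that first appears at Grade 3 on the same day is counted.

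Safety is a primary objective (Section 2.1). The treatment-emergent summaries, by preferred term and worst grade and for Grade 3 or higher and related events, are its main tabulated output.

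**Working it through.** No sample size, power or event figure is involved, and the plan states no number to reproduce. The check sets the collection rules against the counting rule by type of event.

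| Event | Collection required? | Treatment-emergent on the literal wording? |
|---|---|---|
| New onset, first dose to 30 days after last dose | Yes (8.1, 7.4) | Yes |
| Onset before first dose, worsens during dosing | Yes (8.1) | Yes |
| Onset before first dose, worsens after last dose and by Day 30 | Yes (8.1, 7.4) | **No, related or not** |
| New onset after Day 30, related and serious | Yes (8.2) | Yes |
| New onset after Day 30, related and non-serious | **Not required** | Yes, if it is reported |
| New onset after Day 30, unrelated | No | No |

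**Third row: the main point.** The any-time extension for related events sits in parentheses inside the new-onset limb. The worsening limb carries no such extension, so relatedness does not bring the event back in.

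How long the uncounted stretch lasts depends on what being on study medication means:
- If it ends with the last dose, the gap is 30 days.
- If one borrows the weekly-dosing convention in SAP 5.2.1.4, which adds 7 days after the last dose to the duration of treatment, the gap is 30 − 7 = 23 days. That formula was written for exposure, so using it here is an assumption.
- If it is meant to include the 30-day follow-up, the gap is 0 days.

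The text leans against the last reading. The same sentence spells out the 30-day window where it intends one, and SAP 5.3.1 separates being off treatment from being off study.

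**Fifth row: the secondary point.** The extended follow-up of related AEs in Section 7.5 concerns following events to resolution, and Section 10.2 ties it to unresolved events. Neither passage asks for new non-serious events with onset after Day 30.

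**Where the effect stops.** DLTs are defined separately in Section 4.1.4 and confined to Cycle 1, and the RP2D rests on the DLT population (Section 12.2). Laboratory shifts run from baseline to worst grade with no on-medication limit (Protocol 12.5.2; SAP 5.3.4.6.1). SAP Listing 15.2 lists adverse events for the whole Safety population.

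**The case against.** The strongest reply is that the third row may never arise in practice. Preexisting toxicity goes into medical history (Sections 6.2 and 7.1), and each AE record carries its own onset date (Section 9). If a site enters late worsening as an AE dated to the worsening, the new-onset limb counts it and the two windows agree. This stands as far as it goes: the loss depends on the event keeping its pre-dose onset date and on the undefined term excluding the follow-up period. The documents settle neither. But a rule with an explicit limb for pre-dose onset presupposes that some records keep that date.

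A second reply is that a classification rule wider than collection excludes nothing, and that the any-time clause has a working purpose for related SAEs. That also stands. Collecting only related SAEs after Day 30 is a choice of scope. Open-ended passive reporting of non-serious events would bring uneven capture, so its absence is a trade-off and not an error.

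Nor should a reader infer that every related event tabulated after Day 30 must be serious. Section 8 asks investigators to alert the Sponsor to anything unusual, and Section 8.2 lets an investigator's judgment of significance make an event serious. The documents support only that systematic capture is limited to serious events.

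**Conclusion.** The two limbs of the treatment-emergent rule do not match each other, and the worsening limb does not match the collection period. On the literal wording, worsening of a pre-dose event between the last dose and Day 30 is missing from the treatment-emergent tables, though not from the listings or laboratory shifts. The direction is known, since counts can only fall. The number of events is not given and cannot be derived. The conclusion assumes that being on study medication does not extend through the 30-day follow-up and that worsening is not always re-entered as a new AE. The correction is worth making because it is almost free and concerns a primary-objective output. The any-time clause is a lesser matter of disclosure.

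Two stronger inferences are tempting and should not be drawn.
- **Substantial drug remaining at Day 30.** The longest monkey half-life in Section 1.4.1, 470 hours, was seen at 180 mg/kg, which is 180 / 2.5 = 72 times the Cohort 1 dose. Half-life lengthened with dose, and the use of monkey values for humans is a simulation assumption tied to the 20 mg/kg data.
- **Toxicity known to begin after Day 30.** Section 1.3.3.3 reports that "Slight to moderate periorbital swelling was observed primarily during the recovery phase in all IMC-CS4-treated groups". It gives no onset day, and that 6-week recovery period overlaps the 30 days in which new events are collected and counted.

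**What to change.** 1. In Protocol 12.5.2 and SAP 5.2.1.2, replace the worsening condition with: *worsens after the first dose and up to 30 days after the last dose (or at any time if related)*.
2. For related events after Day 30, do one of two things. Either state in the study report that they are captured systematically only if serious, or limit the any-time clause to related SAEs. Whichever is chosen should apply to both limbs, because the wording in item 1 extends the clause to worsening.

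The cost is one phrase in each document and, for item 2, a sentence in the report or a second small edit. No visit, sample or reporting duty is added. Treatment-emergent counts may rise slightly. DLT and RP2D decisions do not change.

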8.2 Serious Adverse Events

Serious adverse event collection begins after the subject has signed the ICF and has received study treatment. If a subject experiences an SAE after signing the ICF, but prior to receiving study treatment, the event will NOT be collected unless the Investigator feels the event may have been caused by a protocol procedure.

Study site personnel must alert the Sponsor or its designee of any SAE within 24 hours of Investigator awareness of the event via a Sponsor-approved method. Alerts issued via telephone are to be immediately followed with official notification on study-specific SAE forms. This 24-hour notification requirement refers to the initial SAE information and all follow-up SAE information. An SAE is any adverse event from this study that results in one of the following outcomes:

- Death;
- Initial or prolonged inpatient hospitalization;
- A life-threatening experience (that is, immediate risk of dying);
- Persistent or significant disability/incapacity;
- Congenital anomaly/birth defect; and/or
- Considered significant by the Investigator for any other reason.

Important medical events that may not result in death, be life-threatening, or require hospitalization may be considered SAEs when, based upon appropriate medical judgment, they may jeopardize the subject and may require medical or surgical intervention to prevent one of the outcomes listed in this definition.

Serious adverse events due to disease progression, including death, should not be reported unless the Investigator deems them to be possibly related to the study drug.

Previously planned (that is, planned prior to signing the ICF) surgeries should not be reported as SAEs unless the underlying medical condition has worsened during the course of the study.

Preplanned hospitalizations or procedures for preexisting conditions that are already recorded in the subject's medical history at the time of study enrollment should not be considered SAEs. Hospitalization or prolongation of hospitalization without a precipitating clinical AE (for example, for the administration of study therapy or other protocol-required procedure) should not be considered SAEs. However, if the preexisting condition worsened during the course of the study, it should be reported as an SAE.

Serious adverse events occurring after a subject has taken the last dose of study treatment will be collected for 30 days after the discontinuation of study treatment, regardless of the Investigator's opinion of causation. Thereafter, SAEs are not required to be reported unless the Investigator feels the events were related to either study treatment or a protocol procedure.

Data on SAEs that occur before the end of trial will be stored in the collection database and the Lilly Safety System. If an Investigator becomes aware of an SAE occurring after the subject's participation in the trial has ended, and the Investigator believes that the SAE is related to a protocol procedure or study drug, the Investigator should report the SAE to the Sponsor, and the SAE will be entered into the Lilly Safety System.

8.3 Suspected Unexpected Serious Adverse Reactions

Suspected unexpected serious adverse reactions (SUSARs) are SAEs that are not listed in the Development Core Safety Information (DCSI) or in the IB and that the Investigator identifies as related to study drug or procedure. The United States 21 CFR 312.32, the European Union Clinical Trial Directive 2001/20/EC, and the associated detailed guidances or national regulatory requirements in participating countries require the reporting of SUSARs. Lilly has procedures that will be followed for the recording and expedited reporting of SUSARs that are consistent with global regulatory regulations and the associated detailed guidances.

8.4 Safety Monitoring

The Sponsor CRP or designee will monitor safety data throughout the course of the study.

The Sponsor CRP or designee will review SAEs within time frames mandated by company procedures. The Sponsor CRP or designee, will, as is appropriate, consult with the functionally independent Global Patient Safety therapeutic area physician or clinical research scientist (CRS), and periodically review trends and laboratory analytes.

If a subject experiences elevated ALT $\geq 5 \times$ ULN and elevated total bilirubin $\geq 2 \times$ ULN, clinical and laboratory monitoring should be initiated by the Investigator. For subjects entering the study with ALT $\geq 3 \times$ ULN, monitoring should be triggered at ALT $\geq 2 \times$ baseline. Details for hepatic monitoring depend upon the severity and persistence of observed laboratory test abnormalities. To ensure subject safety and comply with regulatory guidance, the Investigator is to consult with the Sponsor CRP regarding collection of specific recommended clinical information and follow-up laboratory tests. Refer to Section [6.5](#) for a list of the hepatic monitoring tests to be performed.

All reportable SAEs will be submitted to the FDA in accordance with Title 21 Code of Federal Regulations (CFR) Part 312.32.

8.5 Complaint Handling

The Sponsor collects product complaints on study treatment and drug delivery systems used in clinical trials in order to ensure the safety of study participants, monitor quality, and to facilitate process and product improvements.

Complaints related to concomitant drugs/drug delivery systems are reported directly to the manufacturers of those drugs/devices in accordance with the package insert.

The Investigator or his/her designee is responsible for handling the following aspects of the product complaint process in accordance with the instructions provided for this study:

- Recording a complete description of the product complaint reported and any associated AEs using the study-specific complaint forms provided for this purpose; and
- Faxing the completed product complaint form within 24 hours to the Sponsor or its designee.

If the Investigator is asked to return the product for investigation, he/she will return a copy of the product complaint form with the product.

9 TREATMENT-RELATED ADVERSE EVENTS

Subjects will be closely monitored for treatment-related AEs, especially infusion-related reactions, immune-related adverse events (irAE), periorbital edema, and signs indicative of hepatic impairment, leukocyte alterations, and inflammation. Subjects will be evaluated for AEs at each visit and will be instructed to call their study physician to report any AEs between visits.

Adverse event collection will include verbatim term, onset and resolution dates, action taken, outcome, severity (NCI-CTCAE, Version 4.0 grade), relationship to the study therapy, and, if the event is serious, a clear indication of the seriousness.

9.1 IMC-CS4

9.1.1 Immune-Related Adverse Events

Symptoms occurring during or following infusion of investigational therapy will be defined according to the NCI-CTCAE, Version 4.0.

In the setting of symptoms consistent with irAE occurring following infusion of investigational therapy, investigators are encouraged to refer to [Table 10](#) as a guideline for the management of potential toxicities encountered with immuno-oncology agents. Due to the potential of rapid and serious sequelae associated with irAEs, early intervention with immunomodulatory agents as indicated is encouraged, concurrent with further diagnostic medical evaluations for possible non-immune-related causes of AEs. [Table 10](#) is a guideline for the management of irAEs; local standards may supersede recommendations when deemed appropriate by the Investigator.

Table 10. Guidelines for the Management of Potential Toxicities Encountered with Immuno-Oncology Agents

System Organ Class	Adverse Event	CTCAE, Version 4.0 Grade (if applicable) and/or Symptoms ^a		Treatment Plan ^b
		Grade	Symptoms	
Endocrine	Thyroid issues		Asymptomatic, with TSH <0.5 × LLN or >2 × ULN	Continue drug.
			Symptomatic	Continue drug. Administer thyroid replacement.
	Hypotension, altered mental status, headache, fatigue		Endocrine issues aside from thyroid (for example, hypophysitis)	Withhold drug. Administer steroids (1-2 mg/kg/d prednisone). Resume drug when symptoms resolve and are stable on hormone replacement. In case of adrenal crisis, administer stress-dose steroids.
Gastrointestinal	Diarrhea, abdominal pain, blood in stool	2		Withhold drug for 1 wk. Administer antidiarrheal medication and check etiology. Resume drug when symptoms resolve to Grade ≤1. If >5 days' duration despite antidiarrheals, begin steroids (0.5 mg/kg/d prednisone); can resume drug during taper when symptoms resolve to Grade ≤1.
	Diarrhea, ileus, perforation	≥3		Permanently discontinue drug. Administer steroids (1-2 mg/kg/d prednisone), except if the possibility of perforation exists. If >3 days' duration despite steroids, also administer nonsteroidal immunosuppressive.
	Pancreatitis	1-2		Withhold drug. Administer steroids (1-2 mg/kg/d prednisone). Can resume drug during taper.
		≥3		Permanently discontinue drug.

Table 10. Guidelines for the Management of Potential Toxicities Encountered with Immuno-Oncology Agents

System Organ Class	Adverse Event	CTCAE, Version 4.0 Grade (if applicable) and/or Symptoms ^a		Treatment Plan ^b
		Grade	Symptoms	
Hepatobiliary	Transaminitis, elevated bilirubin		Subjects with baseline AST or ALT $\leq 2.5 \times$ ULN: AST or ALT $> 5 \times$ ULN but $\leq 7.5 \times$ ULN and total bilirubin \leq ULN	Withhold drug. Administer steroids (1-2 mg/kg/d prednisone). Resume drug when AST or ALT $\leq 5 \times$ ULN.
			Subjects with baseline AST or ALT $> 2.5 \times$ ULN and $\leq 5 \times$ ULN: AST or ALT $> 7.5 \times$ but $\leq 10 \times$ ULN and total bilirubin \leq ULN	Withhold drug. Administer steroids (1-2 mg/kg/d prednisone). Resume drug when AST or ALT $\leq 7.5 \times$ ULN.
			Subjects with baseline AST or ALT $\leq 2.5 \times$ ULN: AST or ALT $> 7.5 \times$ ULN or total bilirubin $> 3 \times$ ULN	Permanently discontinue drug. Administer steroids (1-2 mg/kg/d prednisone).
			Subjects with baseline AST or ALT $> 2.5 \times$ ULN and $\leq 5 \times$ ULN: AST or ALT $> 10 \times$ ULN or total bilirubin $> 3 \times$ ULN	Permanently discontinue drug. Administer steroids (1-2 mg/kg/d prednisone).
Nervous	Weakness, paresthesia (for example, Guillain-Barré syndrome, myasthenia gravis)		No impact on activities of daily living (ADL).	Withhold drug. Resume drug when symptoms resolve.
			Impact on ADL.	Withhold drug. Administer appropriate medical intervention and steroids (1-2 mg/kg/d prednisone). Can resume drug during taper.
Respiratory	Dyspnea, hypoxia, pneumonitis	1		Consider to withhold drug. Resume drug when stable.
		2	mild-to-moderate symptoms	Withhold drug. Administer steroids (1-2 mg/kg/d prednisone). Can resume drug during taper.
		≥ 3	Severe	Permanently discontinue drug. Administer steroids (1-2 mg/kg/d prednisone).

Table 10. Guidelines for the Management of Potential Toxicities Encountered with Immuno-Oncology Agents

System Organ Class	Adverse Event	CTCAE, Version 4.0 Grade (if applicable) and/or Symptoms ^a		Treatment Plan ^b
		Grade	Symptoms	
Renal and urinary	Elevated creatinine, decreased urine output, blood in urine, edema	1	<1.5 × baseline	Continue drug.
		2-3	>1.5 × ULN but <6 × ULN or >1.5 × baseline	Withhold drug. Administer steroids (1- 2 mg/kg/d prednisone). If symptoms resolve to Grade ≤1, taper steroids over 1 month. Can resume drug during taper.
		4	>6 × ULN	Permanently discontinue drug. Administer steroids (1-2 mg/kg/d prednisone).
Skin	Rash, pruritus		≤50% skin affected	Withhold drug. If symptoms persist or worsen after 1 wk, administer topical or systemic steroids. Resume drug if rash improves to mild (localized) and steroid dose <7.5 mg.
			Stevens-Johnson syndrome, toxic epidermal necrolysis, necrosis, bullous or hemorrhagic lesions	Permanently discontinue drug. Begin steroids (1-2 mg/kg/d prednisone).

Abbreviations: ADL = activities of daily living; ALT = alanine aminotransferase; AST = aspartate aminotransferase; CTCAE = Common Terminology Criteria for Adverse Events; I.V. = intravenous(ly); LLN = lower limit of normal; TSH = thyroid-stimulating hormone; ULN = upper limit of normal.

^a If definition of grade not specified, use CTCAE, Version 4.0 definition.

^b Treatment plan should always include a thorough workup of the issue to rule out other potential etiologies.

Note regarding steroids: Steroids should be tapered over 1 month after symptoms have resolved; if withheld drug may be resumed (that is, not permanently discontinued), it can be resumed only after taper has begun. Other steroid options (besides those shown in this table) may be administered at equivalent doses. For severe adverse events, administration of I.V. steroids is recommended. In the case of adrenal crisis, mineralocorticoid should be administered in addition to steroids.

